We plan to enroll twenty-four individuals (12 male, 12 female) receiving methadone for OUD. Eligibility criteria: (i) non-methadone opioid positive urine screen (as assessed during standard treatment at APT) or indicated via Utox or self-reported past-month opioid use at screening); (ii) DSM-5 criteria for OUD, as assessed via structured clinical interview (SCID)[66]; (iii) ≥ 3 months of methadone treatment; (iv) eligibility for MRI; (v) age 18-50; (vi) baseline scanning with acceptable motion (i.e., <.15mm frame-to-frame displacement), as in prior work. Retention: APT patients attend clinic on a daily basis to receive methadone and this has contributed to high retention rates (e.g., 86% over three months) in our studies[10, 67] in this population.

7. **Subject classification:** Check off all classifications of subjects that will be specifically recruited for enrollment in the research project. Will subjects who may require additional safeguards or other considerations be enrolled in the study? If so, identify the population of subjects requiring special safeguards and provide a justification for their involvement.

 Children	 Healthy	 Fetal material, placenta, or dead fetus
 Non-English Speaking persons	 Prisoners	 Economically disadvantaged
 Decisionally Impaired fetuses	 Employees	 Pregnant women and/or
 Yale Students	 Females of childbearing potential	

NOTE: Is this research proposal designed to enroll children who are wards of the state as potential subjects?

Yes No

8. **Inclusion/Exclusion Criteria:** What are the criteria used to determine subject inclusion or exclusion?

Write here

- i. Inclusion criteria
 1. non-methadone opioid positive urine screen (as assessed during standard treatment at APT) or indicated via Utox or self-reported past-month opioid use at screening
 2. DSM-5 criteria for opioid use disorder, as assessed via structured clinical interview (SCID)
 3. ≥ 3 months of methadone treatment
 4. Age 18 to 50
- ii. Exclusion criteria
 1. Meet DSM-5 psychiatric classifications for lifetime schizophrenia or bipolar disorder with psychotic features, or exhibit significant current suicidal or homicidal plans and intent such that hospitalization is required

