 2. Failure to pass an MRI screening
 3. Women who are pregnant or nursing
 4. Baseline scanning with excessive motion based on frame-to-frame displacement

9. How will **eligibility** be determined, and by whom? *Write here*

Participants will be recruited via clinician referrals from the APT Foundation, one of the largest methadone providers in CT, consistent with our prior[10, 48] and ongoing work. In

IRB# 2000025618

addition to regular attendance for methadone, APT patients meet regularly with clinicians, as per federal guidelines. As [name] (Co-I) is Director of Research for the APT, he is ideally suited to facilitate participant referral and longitudinal clinical assessment for this study.

Individuals will be informed about the study by their clinician at their regular APT clinic visits and provided with verbal information and brochures containing project information. Interested individuals will contact the study team and set up a screening visit. At the screening visit, eligibility will be determined by members of the research team.

10. Risks: Describe the reasonably foreseeable risks, including risks to subject privacy, discomforts, or inconveniences associated with subjects participating in the research.

Write here

- i. Potential risks: This protocol presents minimal risks to subjects. Possible risks include:
 1. Magnetic resonance imaging: MRI is a non-invasive procedure with minimum anticipated discomfort and a safety screening process. Prior studies have not found any adverse effects of MRI. The possible risks and discomforts of MRI are as follows:
 - a. Claustrophobia
 - b. Acoustic noise
 - c. Metal implants are a risk within the magnetic MRI environment
 - d. Discomfort lying in the MRI scanner
 - e. Very slight warming of the body, tingling or involuntary muscle twitches
 - f. Unknown risk to a fetus
 2. Behavioral assessments: These are all non-invasive and should add no risk. The major disadvantage will be the time taken to complete the questionnaires. Our past experience with these and related measures indicates that they are acceptable to subjects including individuals with substance use disorders.
 3. Urine toxicology test and its result: This is non-invasive and should add no risk. Our past experience indicates that urine screens are acceptable to subjects including individuals with substance use disorders.

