This protocol presents minimal risks to the subjects and Unanticipated Problems Involving Risks to Subjects or Others (UPIRSOs), including adverse events, are not anticipated. In the unlikely event that such events occur, Reportable Events (which are events that are serious or life-threatening and unanticipated (or anticipated but occurring with a greater frequency than expected) and possibly, probably, or definitely related) or Unanticipated Problems Involving Risks to Subjects or Others that may require a temporary or permanent interruption of study activities will be reported immediately (if possible), followed by a written report within 5 calendar days of the Principal Investigators becoming aware of the event to the IRB (using the appropriate forms from the website) and any appropriate funding and regulatory agencies. The investigators will apprise fellow investigators and study personnel of all UPIRSOs and adverse events that occur during the conduct of this research project through regular study emails or via email as they are reviewed by the principal investigators. The protocol's research monitor(s), study sponsors, funding and regulatory agencies, and regulatory and decision-making bodies will be informed of serious and unanticipated and related adverse events or unanticipated problems involving risks to subjects or others will be reported adverse events within 5 days of the event becoming known to the principal investigator.

13. Statistical Considerations: Describe the statistical analyses that support the study design.

Write here

Our previous neurofeedback work showed that data from 10-20 subjects is adequate for demonstrating significant control of activity in a single brain region[13, 65, 68, 69] and that data from two groups of 10-20 subjects is adequate for detecting group differences in control of activity[13, 68]. Our prior CPM work showed that data from N=10 per group is sufficiently powered

IRB# 2000025618

(>.90) to detect differences in connectome-based networks (noncentrality parameter (δ)=5.36, critical t-value=2.10, df=18, power (1- β)=0.99). Finally, we have established retention rates of >85% over 3-months for fMRI studies with methadone patients[10, 70]. Thus, we are confident that a sample size of N=24 (N=12 per group) is sufficiently powered.

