The statistical tests will be as follows: Aim 1: Opioid use will be entered into a linear effects model with the between-subject factor of feedback group (active/sham). Aim 2: Opioid abstinence network strength during resting state and task fMRI runs will be compared between time points using linear mixed models with the between-subject factor of group (active/sham) and the within-subject factor of time (baseline/follow-up scan). Aim 3: Craving and negative affect will be compared using linear mixed effects model with the between-subject factor of group (active/sham) and the within-subject factor of time (baseline/follow-up scan). Associations between craving and negative affect and opioid abstinence network connectivity strength during transfer runs will be tested using Pearson's or Spearman's correlations, as appropriate depending on the distribution of the data. Replication: For replication of our pilot data (Figure 2 of research strategy), Pearson's correlations will be tested between opioid abstinence network connectivity strength at baseline and percent opioid-negative urines across the study.

SECTION II: RESEARCH INVOLVING DRUGS, BIOLOGICS, RADIOTRACERS, PLACEBOS AND DEVICES

If this section (or one of its parts, A or B) is not applicable, check off N/A and delete the rest of the section.

A. RADIOTRACERS N/A

B. DRUGS/BIOLOGICS N/A

C. DEVICES N/A

SECTION III: RECRUITMENT/CONSENT AND ASSENT PROCEDURES

1. Targeted Enrollment: Give the number of subjects:

- a. Targeted for enrollment at Yale for this protocol:
24 completers (individuals participating in all scanning sessions).
- b. If this is a multi-site study, give the total number of subjects targeted across all sites: NA

2. Indicate recruitment methods below. Attach copies of any recruitment materials that will be used.

 Flyers	 Internet/web postings	 Radio
 Posters	 Mass email solicitation	 Telephone
 Letter	 Departmental/Center website	 Television
 Medical record review*	 Departmental/Center research boards	 Newspaper
 Departmental/Center newsletters	 Web-based clinical trial registries	 Clinicaltrials.gov

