 YCCI Recruitment database	 Social Media (Twitter/Facebook):	
 Other:		

IRB# 2000025618

We plan to collect full data from twenty-four individuals (12 M, 12 F) receiving methadone for OUD. Thus, in order to account for possible participant attrition, we will likely scan up to 40 individuals (and anticipate screening up to 100). Participants will be recruited via clinician referrals from the APT Foundation, one of the largest methadone providers in CT, consistent with our prior[48, 49] and ongoing work. While rates of other forms of medication-assisted treatment (e.g., buprenorphine, naltrexone) have increased in recent years, methadone remains the most prevalent treatment for OUD in the US[20], therefore, to reduce sample variability, this study will only recruit individuals treated with methadone. For regular attendance for methadone, APT patients meet regularly with clinicians, as per federal guidelines. [name] (Co-I), Director of Research for APT, is ideally suited to facilitate participant referral and longitudinal clinical assessment for this study.

* Requests for medical records should be made through JDAT as described at
<http://medicine.yale.edu/ycci/oncore/availableservices/datarrequests/datarrequests.aspx>

3. Recruitment Procedures:

- a. Describe how potential subjects will be identified. *Write here*
- b. Describe how potential subjects are contacted. *Write here*
- c. Who is recruiting potential subjects? *Write here*

Consistent with previous studies conducted by the PI and co-investigators, participants in methadone treatment for an opioid-use disorder will be recruited from the APT Foundation. Interested participants entering the methadone treatment program at APT will be referred by APT personnel to research staff when possible for eligibility screening. [name], a co-investigator for this study, is both the Director of Research and the Director of Pain Services for the APT Foundation, he is ideally suited to facilitate participant referral and longitudinal clinical assessment for this study. Participants may also be referred to the study by word of mouth from other participants. HIC approved recruitment materials will provide information about how to contact research staff to learn more about the study. All recruitment will be conducted by local HIC-approved study personnel who completed HIC training requirements.

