Interested individuals will contact the study team and set up a screening visit. The screening visit will be in-person or will be conducted remotely. At the screening visit, eligible participants will be provided a complete description of the study procedures, and then they will be asked to provide informed consent. Due to COVID-19 it may be necessary to obtain informed consent remotely via Yale secure video (e.g., Zoom or Skype for business) or Yale secure online survey software (Qualtrics). A trained member of the research team will perform the informed consent procedure in a private setting. This procedure will include description of the components described in the consent form, including: (i) voluntary nature of participation; (ii) participants may withdraw without consequences to clinic services received; (iii) study purpose and procedures; (v) schedule of study visits; (vi) neuroimaging procedures; (vii) risks and benefits of participation; (viii) potential compensation; (ix) alternatives to study participation; and (x) confidentiality. All potential participants will be allowed to ask questions and given sufficient time to consider the decision to participate. All participants will be given a copy of the consent form. If all study criteria are met and consent is obtained, the individual will be enrolled in the study and schedule their first scanning session. These procedures are in line with policies and procedures of the Yale Institutional Review Board (IRB).

7. Evaluation of Subject(s) Capacity to Provide Informed Consent/Accent: Indicate how the personnel obtaining consent will assess the potential subject's ability and capacity to consent to the research being proposed.

Write here

Comprehension will be assessed during the informed consent process through a verbal interaction between the prospective subject and study personnel obtaining informed consent.

IRB# 2000025618

8. Non-English Speaking Subjects: Explain provisions in place to ensure comprehension for research involving non-English speaking subjects. If enrollment of these subjects is anticipated, translated copies of all consent materials must be submitted for approval prior to use.

Write here

There are no plans to recruit or enroll non-English speaking subjects. There are no provisions in the current protocol to accommodate non-English speaking participants (to translate study documents, assessment battery, informed consent form, or other study material into other languages).

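### Does a target of 24 completers from up to 40 scanned, beside a plan to enroll 24, commit the trial to a completers-only analysis?

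*Combined protocol and SAP*

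**What the plan says.** Three places give a number of participants.

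- Section I.6 (Subject Population): "We plan to enroll twenty-four individuals (12 male, 12 female) receiving methadone for OUD". The same paragraph lists "baseline scanning with acceptable motion" among the eligibility criteria.
- Section III.1 (Targeted Enrollment): "24 completers (individuals participating in all scanning sessions".
- Section III.2 (recruitment methods) seeks full data from 24, with the same split by sex, and adds that "in order to account for possible participant attrition, we will likely scan up to 40 individuals". Up to 100 may be screened.

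Section III.6 (Process of Consent) places enrollment before scanning: "If all study criteria are met and consent is obtained, the individual will be enrolled in the study and schedule their first scanning session". Section I.8 nevertheless excludes for "Baseline scanning with excessive motion based on frame-to-frame displacement", which can be known only after a scan.

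Retention is cited twice: "high retention rates (e.g., 86% over three months) in our studies" (Section I.6) and "we have established retention rates of >85% over 3-months for fMRI studies with methadone patients" (Section I.13). No rate is given for loss to baseline motion.

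For H1a, Section I.4 (Hypothesis testing) measures opioid use as the percentage of negative urines over five weekly visits. It does not say how a missed urine counts. TLFB is collected at the same visits and at one month. For Aim 3, Section I.4 names a repeated measures ANOVA and Section I.13 a linear mixed effects model. Neither section says who is analysed.

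**The concern.** If people are enrolled at consent, everyone scanned is already enrolled, so 24 enrolled cannot stand literally beside up to 40 scanned. A target counted in completers, with no analysis set, could also be read as a plan to analyse only those who attend every scan. Urines are collected at the scan visits, so a missed scan can mean a missed urine.

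At stake is who counts in Aim 1, and with what score. If people who stop early use more opioids than those who finish (plausible, but not stated in the documents), a completers-only percentage of negative urines would look too favourable. A comparison of active with sham would be distorted only if the loss, or the gap between completers and non-completers, differed by arm. If loss is unrelated to opioid use, only precision suffers.

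**Working it through.** **1. The counts side by side.** Sections III.1 and III.2 agree: 24 is the number with full data, and 40 is the most that may be scanned to get there. The sample-size statement in Section I.13 also rests on N = 24. Section I.6 repeats the 24 and the 12/12 split but uses the word enroll. Since it makes acceptable motion on the baseline scan an eligibility criterion, enroll there can mean people who have passed that scan. Section III.6 uses the word for an earlier step. The terms are used loosely, but no third target is created.

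**2. Can the ceiling of 40 be reproduced?** Number needed = 24 / retention, assuming the cited three-month retention applies to attendance at all five scans.

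- 24 / 0.86 = 27.9, so 28. 24 / 0.85 = 28.2, so 29.
- Expected completers from 40: 40 x 0.85 = 34.0; 40 x 0.86 = 34.4.
- Binomial chance of at least 24 completers at 85%: 0.738 with 29 scanned, 0.959 with 32, 0.991 with 34, above 0.999 with 40.

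Retention alone does not give 40, which would correspond to 24 / 40 = 60% completion. But 40 is worded as an upper limit, so it need not equal a derived sample size. The room it leaves for baseline motion is:

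- on expected values, 1 - 0.60 / 0.85 = 29.4% and 1 - 0.60 / 0.86 = 30.2%;
- for a 95% chance of at least 24 (a level the plan does not set), 16.6% at 85% retention and 17.6% at 86%.

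**3. Enrolling exactly 24 without replacement.** Expected completers are 24 x 0.85 = 20.4 to 24 x 0.86 = 20.6. The chance that all 24 finish is 0.85^24 = 2.0% to 0.86^24 = 2.7%. Section III.2 rules this design out, so these figures do not describe the trial.

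**4. The urine denominator.** Take someone who gives 3 of 5 urines, 2 of them negative. The score is 2/3 = 67% on urines provided and 2/5 = 40% with missing counted as positive; a completers-only analysis leaves the person out. The choice matters for that person.

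**5. Size of a completers-only bias.** Completer mean minus overall mean = loss fraction x gap, where the gap is the difference between completers and non-completers. The documents give no gap, so 10-30 points is assumed.

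- 15% loss: 0.15 x 10 = 1.5; 0.15 x 30 = 4.5 points.
- If all 16 of 40 non-completers counted as loss: 0.40 x 10 = 4; 0.40 x 30 = 12 points. Anyone removed for baseline motion is ineligible by design rather than a dropout, so this is an upper case.
- Active/sham contrast with equal gaps: 0 with equal loss; with 10% and 20% loss, 0.10 x 10 = 1 to 0.10 x 30 = 3 points.

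For scale, assume an SD of 30-40 points. The standard error is 30/sqrt(24) = 6.1 to 40/sqrt(24) = 8.2 for one arm of 24. For 12 against 12 it is 30 x sqrt(2/12) = 12.2 to 40 x sqrt(2/12) = 16.3. The 15% and contrast figures lie below one standard error; the top of the 40% case does not.

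**6. The two Aim 3 models.** With two time points and complete data, a repeated measures ANOVA and a random-intercept mixed model ordinarily give the same test of change. They part when a follow-up value is missing, and the dedicated statistics section names the model that can keep such people.

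**The case for a change.** The strongest case for a change is about timing: whether a person who stops early counts, and with what score, could be settled after the data are seen. Aim 1 has only a between-subject factor, so the mixed models for Aims 2 and 3 do not deal with missed urines. Sections I.1 and I.4 describe all 24 as receiving active feedback; on that reading, equal loss across arms cannot cancel the bias. The remedy would be a few sentences, with no added visits.

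The gaps are real, and the point about Aim 1 stands. Three things weigh against a required change. First, a completers-only analysis is inferred from silence: a recruitment target is not an analysis set. Second, the cited retention contradicts any claim that no loss rate is given; what is missing is a rate for all-scan attendance and one for motion. Third, the obvious replacement rules are themselves open to dispute:

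- Scoring on urines provided counts the pre-training baseline urine. That is 1/5 = 20% of a completer's score but 1/2 = 50% for someone who leaves after training scan 1, in a sample selected for recent opioid use.
- Starting the analysis set at training scan 1 drops people whom Section III.6 already counts as enrolled.
- Using every visit for Aim 2 cannot work for the reward and Stroop tasks, which are run only at baseline and follow-up.

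TLFB also gives a second record of opioid use and can cover a missed week if the person returns.

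**Conclusion.** No change to the plan follows. The word enroll in Section I.6 is a slip that Sections III.1 and III.2 resolve, and 40 is an adequate ceiling if the cited 85-86% retention carries over to attendance at all scans. The unnamed analysis set and urine denominator are details that an analyst fills in the ordinary way: include those who stop early, say how missed urines are counted, and show the result under another rule. For Aim 3, the mixed model in Section I.13 serves.

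The possible bias is 1.5-4.5 points in a one-arm level at 15% loss and 0-3 points in an active/sham contrast. It could reach 12 points only if all 16 of 40 non-completers were true dropouts and the gap were 30 points. These sizes rest on gaps and loss patterns that the documents do not give. They show how the choice could matter, not that the plan makes the wrong one.
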